4.4 Sample size calculation

RCT

The primary objective of the study is to realize an efficient allocation of resources to the available treatment options in advanced PD. For this, primarily an economic evaluation will be carried out and the sample size has been calculated accordingly. Society's willingness-to-pay (WTP) per Quality Adjusted Life Year (QALY) may be indicative of whether or not CLI is affordable compared to DBS. The Dutch Raad voor de Volksgezondheid (RvZ) reported a value of €80,000 per additional QALY in 2006 as a potential upper limit of affordability. Explicitly, the figure is reported by the RvZ as a potential, but also unofficial limit: it should

Version 7: 23-10-2019 16 of 48

not be taken as a definite one. Other arguments based on patient preference or access to health care should be taken into account as well. Considering that CLI may be a less invasive intervention and access to health care is easier to facilitate when two interventions can be provided, a more lenient upper limit for the extra societal costs per additional QALY may be appropriate here. We propose a sample size calculation based on a WTP per additional QALY of €120,000 (50% above the RvZ figure). Based on the net health benefit formula suggesting that differences in QALYs between the interventions should be larger than the difference in costs (i.e., €34,174 a year) divided by the maximum WTP (i.e., €120,000 per QALY) in order for one intervention to be accepted as more efficient than another intervention, CLI treatment should at least outperform DBS treatment by 0.2847 QALY per year. Based on literature data with comparable costs estimates, [6] we anticipate standard deviations (SD) for QALYs up to 0.35 and for total costs up to €10,000 (factoring in a 12-month follow-up and non-responders).

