To achieve 80% power and given a two-sided significance level of 0.05, up to 26 patients per group (or 52 in total) are needed to detect a difference of at least 0.2847 QALY for WTP-values up to €120,000 and a worst case scenario of zero correlation between costs and clinical effect, using a two-group t-test. Accounting for a possible dropout of 20%, we will randomize 66 patients (33 per group). With this sample size and given the same test conditions (power, type-I error rate, test chosen, drop-out rate) we are also able to detect a difference in mean PDQ-39 scores between both groups of 11.9, assuming an expected mean score of 32 in the DBS group and a standard deviation of 15.

Motivation for standard deviations for QALY

Literature data [8-10] show that the standard deviation for PDQ-39 scores from operated PD patients equals 15 points and that a 4 to 5 points difference is associated with a QALY difference of approximately 0.1,[16] suggesting a standard deviation for QALYs of up to 0.35.

Patient preference trial

We (conservatively) estimate that during the inclusion period a total of 180 patients (60% of the eligible patients) may decline to participate in the RCT, but are willing to take part in the preference observational study. Based on our clinical experience it is expected that 60% of these patients (n=108) prefers DBS, against 40% (n=72) preferring CLI.

When comparing the effect of DBS treatment of patients who express a preference for that treatment with the effect of DBS treatment in the randomised patients, and given the same test conditions (power, type-I error rate, two group t-test) we are able to detect a difference in

Version 7: 23-10-2019 17 of 48

mean PDQ-39 scores between both groups of 8,4, assuming an expected mean score of 32 in the randomized DBS group and a standard deviation of 15.

In case only 120 patients (40% of the eligible patients) agree to take part in the preference observational study, we are able to detect a difference in mean PDQ-39 scores between both DBS groups of 8,9.

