II - In case both follow-up PDQ-39's were missing (*i.e.*, nine and 12 months) but a baseline PDQ-39 was available, multiple imputation was used by fully conditional specification using predictive mean matching with five data sets and with potentially relevant variables at baseline (*e.g.*, age, sex, PDQ-39), previously observed outcomes and adverse events as predictors. The predictive mean matching imputation was performed separately per treatment group of the mITT population and chosen to ensure that imputed values were in the appropriate range.¹⁸ Additionally, we repeated this imputation of the PDQ-39 for the total mITT population as a scenario analysis.

III - For patients with a missing baseline PDQ-39, the imputation method as described in II was used, with follow-up PDQ-39 score(s) as covariate(s).

Since missing values were expected to be missing not at random, a conformity scenario and multiple worst-case scenarios for the mITT analysis were predefined, making use of additionally gathered data if possible. If lost to follow-up, the patients' treating physicians were asked to provide information on these patients regarding their treatment and functioning at 12 months after start of the allocated treatment (*i.e.*, deceased and if so, cause of death; use of the allocated treatment; use of the alternative than allocated treatment; living at home or in a health care facility; and modified Rankin scale).¹⁹ Loss to follow-up because of clinical improvement was deemed unlikely, therefore the conformity scenario for a patient with a missing 12-month PDQ-39 summary index score was to assign the mean PDQ-39 value in the allocated treatment arm. Possible worst-case scenarios were: (A) to assign the lowest assessed PDQ-39 in both treatment arms, and (B) scenario 1 minus ½ minimal clinically important difference (*i.e.*, ½ of -1,6 as defined in literature).²⁰ Based on the additional data acquired in case of loss to follow-up, the most applicable worst-case scenario was selected and justified.

In case of death, the 9-month follow-up PDQ-39 was carried forward if available. For patients alive at the moment of the 9-month follow-up, but without available PDQ-39 at that moment, the 9-month imputed PDQ-39 was carried forward. In case of death before the 9-month follow-up time point, no PDQ-39 summary index scores were used for this patient.

Secondary outcomes

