For missing health utility data over time among patients alive and for missing data on resource use during follow-up the choice of imputation approach depended on the observed missing data pattern and whether or not missingness was associated with baseline variables or previously observed outcomes. Missingness of data (completely) at random was handled with multiple imputation as described above (see page 10).

In a sensitivity analysis potential missingness of data not at random was addressed to account for the expectation by the treating clinicians that missingness of data may well depend on a worsened health status (see also page 10). The following scenarios were addressed in this sensitivity analysis by shifting the costs and health outcomes from the missingness (completely) at random imputation:

- a) increasing actually imputed costs by 20% and 40%
- b) increasing actually imputed PDQ-39 summary index scores changes by 20% and 40%
- c) decreasing actually imputed QALYs by 20% and 40%
- d) combining a) and b)

e) combining a) and c).

Findings of the clinical analyses might have suggested to explore additional scenarios for the sensitivity of the economical evaluation. The higher its impact, the more extensively the sensitivity analysis was reported in the main text, with the remainder reported in the Supplementary Material.

The handling of missing data applied recommendations by Faria et al.³⁴

Cost-effectiveness

Incremental analysis

Differences in costs and differences in changes in PDQ-39 from baseline between the treatment groups were used to calculate the incremental cost-effectiveness ratio (ICER), again following non-parametric bootstrapping drawing 2,500 samples of the same sizes as the original samples and with replacement to account for sampling variability. Likewise, differences in costs and differences in QALYs were used to calculate the incremental cost-utility ratio (ICUR). Differences in costs and the associated differences in health outcomes were plotted with cost-effectiveness planes,³⁵ for example see Figure EE-1.

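### The economic missing-not-at-random scenarios set no arm-specific shift and no tipping point, so dropout that is more informative in one arm is not tested for QALYs and costs

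*SAP*

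**What the plan says.** The HEAP (Handling of missing data) uses multiple imputation where missingness is taken to be at random. It then adds a sensitivity analysis for data missing not at random, because the treating clinicians expected missing data to go with poorer health. Five scenarios shift the imputed values:

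- (a) "increasing actually imputed costs by 20% and 40" per cent;
- (b) the same percentage increases applied to imputed PDQ-39 changes;
- (c) "decreasing actually imputed QALYs by 20% and 40" per cent;
- (d) a with b, and (e) a with c.

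No scenario names an arm, gives the arms different shifts or searches for a tipping point. The same section allows further scenarios if the clinical findings suggest them, without defining any. It also says that sensitivity analyses with more impact will be reported more fully.

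The outcomes being tested are contrasts between arms: the incremental cost-utility ratio, ICUR (HEAP, Types of economic evaluation), and the net health benefit (HEAP, Incremental analysis). Both are estimated in the modified intention-to-treat (mITT) population only (HEAP, Analysis population).

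Protocol 4.4 gives a scale for judging size: "CLI treatment should at least outperform DBS treatment by 0.2847 QALY per year". That target follows from "the difference in costs (i.e., €34,174 a year") and a "sample size calculation based on a WTP per additional QALY of €120,000".

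**The concern.** A percentage shift applied alike to both arms tests whether the general level of the imputed values matters. It says little about the case that biases a comparison most directly: missing patients who did worse than imputed mainly in one arm. That case is plausible here. The trial is open label, the two treatments are very different procedures, and the SAP reports that comorbidity reduced the completeness of follow-up.

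Direction matters too. With similar imputed shares, and with CLI both dearer and better in QALYs, scenario e can move the result only against CLI, which is also the direction of the trial's hypothesis. Poorer outcomes among missing DBS patients, which would favour CLI, are never isolated. Because reporting depends on impact, a scenario that moves little by construction would be reported briefly and could be taken as reassurance.

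**Working it through.** **1. The plan's own figure.** Protocol 4.4 gives SDs of 0.35 (QALY) and €10,000 (costs), zero correlation, €120,000 per QALY, 80% power and two-sided 0.05.

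- Target: 34,174 / 120,000 = 0.2848, stated as 0.2847.
- SD of net health benefit: √(0.35² + (10,000/120,000)²) = 0.3598.
- n per group by the normal formula: 2 × (1.960 + 0.842)² × 0.3598² / 0.2847² = 25.07, so 26. This agrees with "up to 26 patients per group (or 52 in total) are needed".
- With 20% dropout: 26 / 0.8 = 32.5, so 33 per group and 66 in all, as stated.

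The target and the 20% dropout rate can therefore serve as the scale.

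**2. Formulas.** Let s be the shift, f the imputed share, m the mean imputed QALY and c the mean imputed cost, with subscripts C (CLI) and D (DBS).

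- Change in QALY difference (CLI minus DBS) = −s × (f_C·m_C − f_D·m_D).
- Change in cost difference = +s × (f_C·c_C − f_D·c_D).
- For a one-arm shift, drop the other arm's term.

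Assumptions not in the documents: f = 20% per arm (borrowed from planned dropout; 10% to 30% examined), m = 0.6 (0.4 to 0.8), and annual DBS cost €10,000 to €30,000 with CLI €34,174 dearer. The lower bound is the DBS equipment estimate in Protocol section 1.

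**3. QALYs, common 40% cut, 20% imputed in each arm.**

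- Equal means of 0.6: −0.4 × (0.12 − 0.12) = 0.000.
- CLI better by 0.2847, imputed means equal to arm means: −0.4 × 0.2 × 0.2847 = −0.023. The difference is multiplied by 1 − 0.4 × 0.2 = 0.92 and cannot change sign.

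**4. QALYs, 40% cut in one arm, 20% imputed.**

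| Mean imputed QALY | Change in difference | At €120,000 | Share of 0.2847 |
|---|---|---|---|
| 0.4 | 0.032 | €3,840 | 11% |
| 0.6 | 0.048 | €5,760 | 17% |
| 0.8 | 0.064 | €7,680 | 22% |

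The sign is negative for CLI only and positive for DBS only.

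**5. QALYs, common 40% cut, unequal imputed shares, means 0.6.**

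| Imputed CLI / DBS | Change in difference |
|---|---|
| 25% / 15% | −0.024 |
| 30% / 10% | −0.048 |
| 10% / 30% | +0.048 |

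Here the shifts do not cancel.

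**6. Costs, common 40% increase, 20% imputed in each arm.** 0.4 × 0.2 × 34,174 = €2,734, or 0.023 QALY at €120,000. This is an upper limit, because items taken from hospital records may need no imputation.

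**7. Costs and QALYs together (scenario e), 40%, 20% imputed, mean QALY 0.6 in both arms.**

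| Shift applied to | Change in net health benefit (QALY) |
|---|---|
| Both arms | −0.023 |
| CLI only | −0.077 to −0.091 |
| DBS only | +0.055 to +0.068 |

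For example, CLI only with DBS at €10,000 gives −0.048 − 0.08 × 44,174 / 120,000 = −0.077. DBS only gives +0.048 + 0.08 × 10,000 / 120,000 = +0.055.

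If instead the imputed means follow arm means and CLI is better, the common shift multiplies the cost difference by 1.08 and the QALY difference by 0.92. The ICUR then rises by 1.08 / 0.92 − 1 = 17%. The decision at €120,000 changes only if the base ICUR lies between about €102,200 (120,000 × 0.92 / 1.08) and €120,000.

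**The case against.** The near-cancellation depends on the inputs. It needs similar imputed shares and similar imputed QALYs. PDQ-39 imputation is run separately by treatment group, and if QALYs are handled likewise, equal percentages need not be equal absolute shifts. Step 5 shows that a 30%/10% split moves the difference as much as a one-arm shift does. Cost shifts do not cancel at all if CLI costs more. This stands: the scenarios do test something, and the point must be stated conditionally.

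The size is also modest. With SD 0.35 and 26 per arm, the standard error of the QALY difference is 0.35 × √(2/26) = 0.097, so 0.048 is about half a standard error. Utilities are measured at several visits, so a patient who misses some of them has only part of the year imputed, which makes 0.048 an upper bound. This stands too and keeps the point minor.

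The plan has related safeguards. It allows further economic scenarios, asks treating physicians about patients lost to follow-up, and adds conformity, worst-case and best-case scenarios in the clinical part. But the economic extras are undefined, and the clinical scenarios concern PDQ-39, not QALYs or costs.

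Three stronger readings are tempting, and the documents support none of them:

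- *The CLI refusals show that missingness will be unequal.* Patients who refused their allocation are outside the mITT population (SAP, Analysis populations; Appendix I), so they have no imputed QALY or cost for these scenarios to shift. The documents do not report missingness by arm within the mITT.
- *Clinical worst case A has the same defect.* It is "to assign the lowest assessed PDQ-39 in both treatment arms": a fixed observed PDQ-39 score, not a percentage shift and not an economic outcome.
- *The scenarios cannot show any effect of informative dropout.* Scenarios a, d and e move the cost difference, and e can change the decision within the range in step 7. Even the common shift in both arms is inferred from the absence of an arm label; the text does not state it.

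**Conclusion.** The point holds in conditional form, as an optional improvement. Scenario c, and its combination with costs in e, prespecify neither an arm-specific shift nor a tipping point. Where imputed shares and imputed QALYs are similar in the two arms, the QALY shifts nearly cancel, and the planned set omits the one-arm case. That case is worth up to about 0.048 QALY for a 40% cut, roughly a sixth of the planning target, on assumed values of 20% imputed and a mean imputed QALY of 0.6. The scenarios do not test whether dropout that is more informative in one arm would alter the cost-utility conclusion. Nothing in the documents shows that such dropout occurred.

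**What to change.** In the HEAP, state which arm or arms each shift applies to, and run every QALY and cost shift three ways: both arms, CLI only and DBS only. Add two combined scenarios: the one least favourable to CLI (lower QALYs and higher costs in CLI only) and the one least favourable to DBS (the same in DBS only). Report the share of imputed QALY and cost data by arm, and the pair of arm-specific shifts at which net benefit at €120,000 per QALY changes sign.

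This reuses the existing imputations and needs no new data. The cost is extra runs and a longer supplementary table.

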Another treatment option for patients with advanced PD is Continuous subcutaneous Apomorphine Infusion (CAI). In the Netherlands CAI is used in a smaller number of patients. CAI is not included in this research protocol, because at start of this trial, the evidence for effectiveness of CAI was of poor quality. Besides, CAI is slightly more expensive than DBS. A study that directly compares all three treatments is not feasible because of the large sample size needed.

Both treatment with DBS and CLI is expensive. We estimate that DBS equipment and batteries cost €10,000 per patient/year and CLI equipment and infusion solutions cost

Version 7: 23-10-2019 10 of 48

€45,000 per patient/year. In addition, patients need surgery and they frequently visit the clinic. In a recent Spanish study the mean cumulative 5-year cost per patient (including the surgery) was estimated € 88,014 for DBS and € 233,986 for CLI. [6]

Several level I studies have shown that DBS is efficacious for the treatment of PD motor symptoms: it reduces dyskinesias and motor fluctuations.[7] CLI reduces off-time and is effective for the treatment of motor fluctuations and dyskinesias as was shown in a few small and one larger level I trial. Both therapies significantly improve quality of life.[7-13] No head-to-head comparison of DBS and CLI has been performed, but when comparing individual studies, the effects on quality of life are similar.[8, 13] Little is known about comparative adverse-effects profiles of the therapies. One retrospective study suggests a higher rate of complications in CLI.[14]

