The primary health outcome in the cost-effectiveness analysis was the change in the PDQ-39 between baseline and 12 months after randomization. The change score showed the increase or decrease in number of difficulties across eight different dimensions of health (including mobility, activities of daily living, emotional well-being, and stigma) as experienced by patients in the preceding month. Dimension scores are coded on a scale of 0 (perfect health as assessed by the measure) to 100 (worst health as assessed by the measure). The change score was defined as the mean score on the eight scales at month 12 minus the mean score at baseline, in theory ranging from -100 to +100 with a score of 0 representing 'no change'.

The primary health outcome in the cost-utility analysis was the number of QALYs. Patient's health status was assessed with the EQ-5D-3L at baseline, one week, three months, six months, nine months, and 12 months post randomization. The EQ-5D contained five items: mobility, self-care, usual activities, pain/complaints, and mood (anxiety/depression).³¹ Each item had three response options: no problems, some problems, or serious problems. EQ-5D scoring profiles at successive measurements were converted into health utility scores using general population based tariffs of time trade-off ratings of health states.³² QALYs were calculated by taking the product sum of the health utility scores during follow-up and the interval lengths in years in-between successive measurements.

Health economic analysis methods

Analysis population

The CEA and CUA were done with the modified intention-to-treat population (see page 9) with references to the CONSORT-flow diagram in Figure SAP-1 and the baseline characteristics of the two RCT-subpopulations in Table EE1. Summary statistics for health utility scores at baseline were included in the manuscript text.

Cost-effectiveness threshold

The applied cost-effectiveness threshold for the sample size calculation was €120,000 as described and substantiated in the published study protocol.¹

Statistical decision rules

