For each of the 2,500 bootstraps the net health benefits (NHB) of CLI versus DBS were calculated based on the ICERs for different levels of willingness-to-pay up to €3,000 per additional unit decrease in change in PDQ-39 (NHB_{PDQ-39}), respectively based on the ICURs for willingness-to-pay levels up to €160,000. Cost-effectiveness acceptability curves were plotted to represent uncertainty,³⁶ showing the probability of CLI being cost-effective in comparison with DBS at each level of willingness to pay, see Figure EE-2.

Subgroup analyses

Considering the limited patient numbers, potentially uneven distributions of baseline characteristics despite randomization were exploratory addressed by subgroup analyses for hypothesis generation. Also, a preplanned subgroup analysis by median age was performed to detect a potential influence of being more vulnerable at a higher age.

Additional sensitivity analyses

Apart from addressing the uncertainty of missing data structures, additional sensitivity analyses were performed for the lengths of the life cycles of the DBS and CLI equipment and corresponding depreciation period (6 to 8 years in steps of 1 year versus 5 years).

Scenario analyses

A scenario analysis for the ICUR was performed to correct for health utility scores at baseline by subtracting for each patient the baseline score from the calculated QALYs during the follow-up of 12 months. Another scenario analysis was done to report the ICUR from an international perspective by applying the time trade-off based on valuation of health states based on preferences from the UK general population to the EQ-5D-3L health status profiles and conversion of Euros into English Pound by applying purchasing power parities from the Organisation of Economic Cooperation and Development (or 0.688 divided by 0.772 in 2020).^{37,38}

Table EE2a. Mean per patient use of hospital resources by strategy*

	CLI (n=)	DBS (n=)	Difference** CLI vs DBS
	Mean (95% BCa CI)	Mean (95% BCa CI)	Mean (95% BCa CI)
Screening for suitability			
preop. outpatient consultation			
inpatient stay			
on-/off-phase evaluation			
evaluation / nasogastric tube			
vitamin examinations			
other laboratory			
preop. anesthetic evaluation			
EKG			
MRI-brain	NA		
Continuous Levodopa Infusion			
CLI-pump			
CLI-cassettes			
PEG-jejunostomy placement			
tube replacement			
Deep Brain Stimulation			
(re)implantation			
electrode replacement			
extension cable replacement			
battery exchanges			

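### HEAP missing-data scenario b scales a signed PDQ-39 change without fixing its direction; read as multiplication, it enlarges imputed improvements when it should test worsened health

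*SAP*

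**What the plan says.** The HEAP, under Health outcomes, fixes the direction of the scale: "Dimension scores are coded on a scale of 0 (perfect health as assessed by the measure) to 100 (worst health as assessed by the measure"). It then gives the sign of the outcome: "The change score was defined as the mean score on the eight scales at month 12 minus the mean score at baseline". A negative change is therefore an improvement and a positive change a deterioration. The Incremental analysis section agrees, because it values the PDQ-39 result "per additional unit decrease in change in PDQ-39".

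Under Handling of missing data, the HEAP adds a sensitivity analysis for data missing not at random. The stated reason is "the expectation by the treating clinicians that missingness of data may well depend on a worsened health status". Values from the missing-at-random imputation are to be shifted in five scenarios:

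- a raises imputed costs by 20% and 40%;
- b is "increasing actually imputed PDQ-39 summary index scores changes by 20% and 40" per cent;
- c lowers imputed QALYs by the same percentages;
- d applies a with b;
- e applies a with c.

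Nothing in the HEAP says whether the percentage in b applies to the signed change, to its absolute size or to the month-12 score.

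The protocol's introduction says of DBS and CLI: "Both therapies significantly improve quality of life".

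**The concern.** A percentage change has a fixed direction only when the quantity has a fixed sign. Costs cannot be negative and 12-month QALYs are normally positive, so scenarios a and c reliably describe a sicker patient. The PDQ-39 change runs either side of zero, so a percentage increase has no fixed direction.

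Taken as multiplication, scenario b gives a lost patient with an imputed improvement even more improvement. The plan fears that these patients are the sicker ones. Scenario d then joins higher costs to a better PDQ-39 result, which does not describe a patient who has deteriorated.

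Cost per unit of PDQ-39 is one of the two primary economic outcomes. At stake is whether its pre-specified percentage-shift analysis tests the result in the direction stated. If it does not, an unchanged result under b or d says little about informative dropout.

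**Working it through.** The plan gives no figure that depends on this rule, so there is nothing to reproduce. The check applies the rule as written.

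**Inputs from the documents.** Higher PDQ-39 is worse and change is month 12 minus baseline (HEAP, Health outcomes). The factors are f = 0.2 and 0.4 (HEAP, Handling of missing data). Dropout of 20% is the design allowance, and the PDQ-39 SD is 15, stated for scores and not for changes (protocol 4.4).

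**Assumptions.** The mean imputed change μ is not in the documents, so a range is shown. The share of an arm imputed, p, is set at 20%, borrowed from the dropout allowance.

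**Step 1: single values.** Multiplication gives change × (1 + f). A shift that always worsens health gives change + f × |change|.

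| Imputed change | × 1.2 | × 1.4 | Towards worse, 20% | Towards worse, 40% |
|---|---|---|---|---|
| -20 | -24 | -28 | -16 | -12 |
| -10 | -12 | -14 | -8 | -6 |
| -5 | -6 | -7 | -4 | -3 |
| +5 | +6 | +7 | +6 | +7 |
| +10 | +12 | +14 | +12 | +14 |

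The two rules agree for deteriorations and move in opposite directions for improvements.

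**Step 2: one arm's mean.** Multiplication takes the mean imputed change from μ to (1 + f)μ, so the arm mean moves by p × f × μ. With p = 0.20:

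| μ | f = 0.2 | f = 0.4 |
|---|---|---|
| 0 | 0 | 0 |
| -5 | -0.20 | -0.40 |
| -8 | -0.32 | -0.64 |
| -10 | -0.40 | -0.80 |

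Every non-zero entry is a move towards better health. At μ = 0 the scenario tests nothing on average.

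**Step 3: between arms.** The ICER uses the difference between arms, which moves by f × (p₁μ₁ − p₂μ₂). With equal shares and equal means this is zero. With 20% imputed in one arm, 10% in the other and μ = -8 in both, it is 0.2 × (0.20 − 0.10) × (-8) = -0.16 points, or -0.32 at 40%.

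**Step 4: what a directional test would do.** Suppose imputed changes are normal with SD 15 (assumed to hold for changes) and 20% of the arm is imputed. By simulation, the rule change + f × |change| moves the arm mean by about +0.58 and +1.16 points at μ = -10. At μ = 0, where multiplication gives nothing, it moves it by +0.48 and +0.96.

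**Step 5: scale.** The largest single-arm movement in step 2, 0.80 points, is half the 1.6-point minimal important difference that the SAP uses in its missing-data section. At the top of the HEAP's willingness-to-pay range it is worth 0.80 × €3,000 = €2,400 per patient. The protocol's sample-size section assumes a cost difference of €34,174 a year.

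**The case against.** The strongest reply is that the authors plainly have the direction right. They state that higher is worse, value a decrease, describe the scenarios as shifts and give worsened health as the reason. In that context, increasing a signed change could mean moving it upward by a fifth of its size, from -10 to -8, as intended. This reading is possible, so a reversal is not proven. But the HEAP does not state it, and the usual meaning of raising a value by 20% is to multiply by 1.2. Two analysts could code opposite shifts from the same line.

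Three further replies have weight:

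- **Other checks exist.** The HEAP sends missing PDQ-39 data to the clinical plan's section on missing data, which has a conformity scenario, worst-case scenarios and information from treating physicians. It also allows extra scenarios prompted by the clinical findings. Scenario b is therefore not the only protection, although these rules do not repair b or d.
- **The imputed share may be below 20%.** The analysis uses the modified intention-to-treat population, which leaves out patients who refused their allocation. Some missing month-12 scores are filled from month 9, and deaths before month 9 contribute no score.
- **Imputed changes need not be mostly negative.** The imputation model uses adverse events and earlier outcomes as predictors, so lost patients may not share the average improvement. If their imputed mean is positive, multiplication moves it the intended way.

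**Conclusion.** The point stands as a defect in the wording of scenarios b and d. The rule does not fix its direction. On its ordinary reading, it works against its stated purpose in any arm whose imputed mean change is negative. That is the expected case if both therapies improve quality of life, but the documents do not guarantee it. Scenarios a, c and e, and so the QALY sensitivity runs, are unaffected.

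The size is modest and rests on assumed values of p and μ: 0 to -0.4 points in one arm's mean at 20% and 0 to -0.8 at 40%, with partial cancellation between arms unless imputation is unbalanced.

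A reader might infer more than this, in three ways:

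- **That the test is reversed for every patient.** It is not; imputed deteriorations move the right way.
- **That the error is twice as large.** At -8 the gap between multiplying (-9.6) and the opposite shift (-6.4) is 3.2 points, but that compares two alternative rules. The movement from the base case is 1.6.
- **That the cost-effectiveness conclusion would change.** The documents do not show this. At €3,000 per point, the assumed cost difference of €34,174 corresponds to about 11.4 points, far more than anything here.

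**What to change.** Rewrite scenario b to say that imputed PDQ-39 values always move towards worse health, and give the formula. Two forms would do:

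- **Proportional:** change + 0.2 × |change| and change + 0.4 × |change|. This keeps the present percentages and corrects only the sign.
- **Additive:** add a pre-specified number of points to the imputed month-12 summary index, cap it at 100 and recompute the change. This is preferable because it still tests something when an imputed change is near zero.

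The size of an additive shift is for the sponsor to choose and justify. Adding 20% and 40% of the month-12 score would be much harsher than a sign correction. At the protocol's expected DBS score of 32 it adds 6.4 and 12.8 points, against 1.6 and 3.2 for the same percentages of a change of -8.

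Use the same rule in scenario d. State also whether month-12 scores filled from month 9 count as imputed. If b and d have already been run by multiplication, report that and rerun them. The cost is one line of text and one of syntax, with no new data.
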